#### Phase II:

Patients will be randomized in a 1:1 ratio either to Arm A, to be treated at the RP2D of BI 836858 plus BSC or Arm B, BSC alone, per Investigator's choice. Patients can be enrolled at any time during this trial without observation period.

Patients randomized to Arm B (BSC alone) have the opportunity to cross-in to receive BI 836858 study drug after 4 months of treatment (EOC4) have elapsed since Cycle 1 Visit 1, following a disease assessment confirmation at this visit, if patients have not progressed to high-risk MDS or AML. At the time-point of cross-in patients must meet all

**Proprietary confidential information.**

© 2019 Boehringer Ingelheim International GmbH or one or more of its affiliated companies. All rights reserved.

This document may not - in full or in part - be passed on, reproduced, published or otherwise used without prior written permission.

inclusion/exclusion criteria, which includes stopping of any ESA and/or iron chelation therapies.

#### 4.1.4 Drug assignment and administration of doses for each patient

Prior to inclusion of a new patient during the cohort dose escalation phase, the Investigator has to confirm the actual dose tier of BI 836858 for the patient with the Sponsor who oversees the cohort dose escalation steps and the safety data of patients from all trial sites. BI 836858 will be administered as an intravenous infusion every 14 days under the supervision of the Investigator or designated personnel.

BI 836858 may be administered at any time during the day.

it is recommended to

start the infusion during the morning hours.

Premedication to prevent infusion-related reactions is obligatory 30 minutes (up to 120 min before start of administration of BI 836858 is permissible) prior to the first and second administration of BI 836858, unless a contraindication for premedication exists, and should include:

- Acetaminophen/Paracetamol 650 mg - 1000 mg p.o., or equivalent
- Antihistamine p.o. or i.v., equivalent to Diphenhydramine 50 mg i.v.
- Glucocorticoid i.v., equivalent to prednisolone 100 mg

If BI 836858 has been well tolerated without signs of infusion-related reactions in the first administration, glucocorticoid premedication may be reduced to a dose equivalent to 50 mg prednisolone for the second through fourth administrations, and in case this is well tolerated reduce the glucocorticoid with the 5th infusion (25 mg with the 5th and 0 mg with the 6th infusion.) However, in case an administration of BI 836858 was not well tolerated the premedication with prednisolone can be re-escalated up to 100 mg.

Before the administration of BI 836858, adverse events and safety laboratory will be assessed. To start or continue treatment with further administrations, all of the following criteria must be met:

- (1) Neutrophils  $\geq 1000 /\mu\text{L}$  ( $1.0 \times 10^9/\text{L}$ )
- (2) Platelets  $\geq 50,000 /\mu\text{L}$  ( $50 \times 10^9/\text{L}$ ), unless CTCAE Grade 3 or 4 thrombocytopenia was preexistent prior to trial entry. Patients who go from Grade 3 to Grade 4 thrombocytopenia after treatment may continue on study provided that post-transfusion platelet count is at least 20,000/uL before therapy is given.
- (3) Acceptable tolerability (in case of an AE at the planned start of a further administration, patients may continue therapy only after recovery to a level which would allow further therapy, i.e. CTCAE grade 1 or baseline value.)

Proprietary confidential information.

In case criterion 1 and 2 are not fulfilled, blood counts and/or the adverse event should be re-evaluated for up to three weeks and documented in the eCRF. In case of a treatment delay, the Sponsor must be notified.

Administration of the trial drug has to be stopped temporarily in case of a DLT (see [Section 5.2.1.1](#)). Patients may continue therapy only after recovery from the DLT to a CTCAE level which allows further therapy based on Investigator assessment and only with a reduced dose of BI 836858. The new dose of BI 836858 must be finally agreed on between the Sponsor and the Investigator. The reduced dose will be valid for all following treatment cycles in the individual patient. A reduction of the dose will be allowed only once for an individual patient during the whole trial. In case a patient experiences a second episode of DLT with the reduced BI 836858 dose, the treatment has to be permanently discontinued. Likewise, treatment has to be discontinued in case the DLT is not reversible. Patients who discontinue treatment will complete an End of Trial Visit and follow-up visits.

Intra-patient dose escalation may be considered after agreement between investigator and sponsor for selected patients. It is restricted to patients who have completed and received a minimum of 8 administrations of BI 836858 and tolerate the treatment well at the time of dose escalation. Intra-patient dose escalation can only be performed at a time when the next higher dose cohort has been reviewed and considered safe by the DSB. The dose escalation step is limited to the dose which has been administered to the next higher cohort. Only one dose escalation will be permitted for a patient. Dose escalations can only occur on Day 1, or Visit 1 of a cycle. After the first dose at the higher dose level, patients have to be monitored for at least 24 hours after the end of the infusion, including a safety laboratory 24 hours after the first administration of the escalated dose of BI 836858. Patients who have escalated to a higher dose and who experience toxicities may be permitted to reduce back to a lower dose, following the criteria described above. A log of all patients pre-screened and enrolled into the study (i.e. having given informed consent) will be maintained in the Investigator Site File (ISF) at the investigational site irrespective of whether they have been treated with investigational drug or not.

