## FLOW CHART 1 – INTRODUCTION TREATMENT

Trial Periods	Screen	Introduction Study Treatment							FU	
	Screen	Cycles 1 - 4 (1 Cycle = 28 days)				EOC4	Cycles 5 & 6**		EOT	FU (No further visits after EoR period upon implementation approval of CTP version 5.0)
Visit	1	Cx V1	Cx V2	Cx V3	Cx V4	C4 V5	Cx V1	Cx V2		
Days (in respective cycle)*	-21 to -1	1	8 ± 1 	15	22 ± 1 	28 ± 2	1	15		
Informed consent	x									
Demographics and baseline conditions	x									
Medical history	x									
Review of in-/exclusion criteria	x	x 								
Dose assignment (Phase I)	x 									
Randomization (Phase II)	x 									
LABS/SAFETY ASSESSMENTS										
Safety laboratory parameters incl. urinalysis 	x	x	x 	x	x 	x	x 	X 	x 	
Physical examination ECOG performance status	x	x 				x	x 		X 	
Vital signs, height  , weight	x	x	x	x	x	x	x 	x 	x 	
Serum pregnancy test 	x	x				x	x		x	
12 lead-ECG	x	x				x	X 		x 	
Adverse events	x	x	x	x	x	x	x	x	x 	
Concomitant therapy	x	x	x	x	x	x	x 	x 	x 	
DISEASE ASSESSMENTS										
Number of transfusions received	x	←-----					x 	-----→		

Proprietary confidential information.

© 2019 Boehringer Ingelheim International GmbH or one or more of its affiliated companies. All rights reserved.

This document may not - in full or in part - be passed on, reproduced, published or otherwise used without prior written permission.

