**FLOW CHART 1 – INTRODUCTION TREATMENT (cont.)**

Trial Periods	Screen	Introduction Study Treatment							FU
	Screen	Cycles 1 - 4 (1 Cycle = 28 days)				EOC4	Cycles 5 & 6**		EOT
Visit	1	Cx V1	Cx V2	Cx V3	Cx V4	C4 V5	Cx V1	Cx V2	
Days (in respective cycle)*	-21 to -1	1	8 ± 1 	15	22 ± 1 	28 ± 2	1	15	
Bone marrow aspiration 	x					X 		X 	X 
Cytogenetics and molecular genetics of MDS 	x					X 			X 
Clinical disease assessment 						x		X 	

TRIAL MEDICATION									
Drug Administration (BI 836858)		x			x			x	x
Best Supportive Care (Phase II Arm B only)		←		x	→				
Eligibility for subsequent cycles of study treatment		X 		X 		X 		X 	X 
End of trial treatment									X 
Other therapies for MDS (Phase II Only)									
Vital Status									X 

EOC4: End of Cycle 4. Patients with clinical benefit, PR or CR after the 4th Cycle and who are tolerating the study treatment may continue on and into the maintenance treatment cycles until PD or other withdrawal criteria are met as noted in [Section 3.3.4.1](#). For patients who have received 8 administrations of BI 836858, this visit will

Proprietary confidential information.

© 2019 Boehringer Ingelheim International GmbH or one or more of its affiliated companies. All rights reserved.

This document may not - in full or in part - be passed on, reproduced, published or otherwise used without prior written permission.

be performed 14 days ( $\pm 2$  days) after the 8th administration of BI 836858. For those patients who received less than 8 administrations, but still in remission, this visit is to be performed 4 months ( $\pm 2$  days) after Cycle 1 Visit 1. Phase II: For patients randomized to BSC, this visit is to be completed 4 months ( $\pm 2$  days) after Cycle 1 Visit 1.

**EOT:** End of Treatment. The EOT visit is to occur 30 days (+7 days) after the last administration of BI 836858. Patients who permanently discontinue study treatment will complete the EOT and complete Follow-up visits. Refer to [Section 3.3.4](#) for treatment discontinuation criteria. After implementation of CTP version 5.0, no further follow-up visits after End of Residual Effect (EoR), unless follow-up is for S(AE) that occurred before EoR period.

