- 18 Can be performed up to 2 days prior to this visit.
- 19 At the EOC4, patients will be evaluated to determine if they have clinical benefit, as defined by IWG objective response (PR or CR) or subjective response (in the absence of objective response) and are tolerating the infusions well and who would like to continue to receive infusions until PD or other criteria for withdrawal are met as noted in [Section 3.3.4.1](#). For each infusion past the 4th cycle, patients will continue to be assessed after each cycle for clinical benefit (objective or subjective response), and that they are tolerating the infusions well and would like to continue until PD or other criteria for withdrawal are met as noted in [Section 3.3.4.1](#).
- 20 Procedures/assessments not mandatory after implementation of CTP version 5.0, but assessments (e.g. hematology & biochemistry laboratory tests, bone marrow aspirates) should be performed at the investigator's discretion, based on standard medical care. Findings are documented in the eCRF only if qualifying for and (S)AE.
- 21 After implementation of CTP version 5.0, vital signs are mandatory only at the day of administration of BI 836858, results will be documented in the eCRF only if qualifying for an adverse event.
- 22 After implementation of Protocol version 5.0, Collection of Concomitant Therapy information only if the indication is treatment of an Adverse Event.

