## 5.2 SAFETY

Recruitment in this trial was discontinued prematurely during the Phase I expansion cohort. With the aim to minimize the burden for trial participants, after approval of CTP version 5.0, the mandatory protocol procedures described below in [sections 5.2.2](#) Assessment of adverse events, [5.2.3](#) Assessment of safety laboratory parameters [5.2.4](#), Electrocardiogram, [5.2.5](#) Assessment of other safety parameters, and [5.3.1](#) Physical Examinations are reduced for all patients who continue to receive trial medication in treatment cycles  $\geq 5$ . Instead, safety assessments should be performed at the investigator's discretion, based on standard medical care. For details refer to Flow Chart.

Findings are documented in the eCRF only if qualifying for an adverse event (see [section 5.2.2](#), which remains unchanged).

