### 5.2.3 Assessment of safety laboratory parameters

#### 5.2.3.1 General safety laboratory parameters

Blood samples and urine have to be collected at the time points specified in the [Flow Chart](#). Safety laboratory examinations will include hematology, biochemistry, coagulation and qualitative urine analysis:

Hematology	Hemoglobin, red blood cell count (RBC), white blood cell count (WBC) with differential (neutrophils, basophils lymphocytes, monocytes, eosinophil), platelets (PLT)  Reticulocytes have to be measured only at Visit 1 of every second cycle, EOC4, EOT.
Biochemistry	Glucose, sodium, potassium, calcium, inorganic phosphate, creatinine, AST, ALT, alkaline phosphatase (AP), lactate dehydrogenase (LDH), bilirubin, urea (preferred) or BUN, total protein, albumin, uric acid  Serum immunoglobulin levels (IgG, IgM, IgA) and direct antiglobulin (direct Coombs) test have to be measured only every 2 cycles, EOC4 and EOT.
Coagulation	Activated partial thromboplastin time (aPTT), prothrombin time (PT), international normalised ratio (INR) where indicated (e.g. treatment with vitamin K antagonists)
Urine	pH, glucose, erythrocytes, leukocytes, protein, nitrite will be analysed by dipstick and reported as semiquantitative measurements. In case of pathological findings, further evaluation should be performed and results documented.
Pregnancy test	A serum pregnancy test needs to be obtained at the time points indicated in the Flow Chart in patients of childbearing potential.

Additional safety labs will be collected on day 2 of Cycle 1 (i.e., 24 hours after the first administration of BI 836858) and after the first infusion of a higher dose, following intra-patient dose escalation (i.e. 24 hours after the first administration of the higher dose). Other lab tests to be included for these visits: haptoglobin, direct antiglobulin/Coombs test, bilirubin (direct and indirect) and free hemoglobin. Non pre-existing abnormal laboratory values (CTCAE Grade 3 or higher) will be followed up every 48 hours until these laboratory values are back to at least CTCAE Grade 1 or baseline.

In case an administration is delayed due to an AE, the patient should visit the site at least once a week for assessment of safety laboratory and AEs. More frequent visits may be appropriate as assessed by the Investigator.

Proprietary confidential information.

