### 6.2 DETAILS OF TRIAL PROCEDURES AT SELECTED VISITS

The investigations as outlined in the [Flow Chart](#) will be performed at the respective visits as described in detail in the following sections. All assessments should be performed prior to dose administration on dosing days, unless otherwise specified.

With the aim to minimize the burden for trial participants, after approval of CTP version 5.0, the mandatory protocol procedures are reduced for all patients who continue to receive trial medication in treatment cycles  $\geq 5$ . Instead, safety assessments should be performed at the investigator's discretion, based on standard medical care. Refer to updated Flow Chart for specific requirements during treatment period.

Findings during safety assessments are documented in the eCRF only if qualifying for an adverse event (see [sections 5.2.2](#), which remain unchanged).

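### From Cycle 5, protocol version 5.0 makes the pre-dose safety laboratory optional, while section 4.1.4 still makes each infusion conditional on neutrophil and platelet counts

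*Protocol*

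**What the plan says.** **The dosing condition.** Protocol section 4.1.4 states "Before the administration of BI 836858, adverse events and safety laboratory will be assessed" and continues "To start or continue treatment with further administrations, all of the following criteria must be met". The criteria are neutrophils of at least 1000/µL, platelets of at least 50,000/µL (with the exception for thrombocytopenia present before entry) and acceptable tolerability. Nothing restricts them to early cycles or exempts treatment under version 5.0.

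**The source of the counts.** In the available text, the hematology panel in section 5.2.3.1 is the only routinely scheduled one that lists both neutrophils and platelets. Sections 6.2.2.4 (Cycles 5 and 6) and 6.2.2.5 (maintenance) still list this safety laboratory among the items to be done before each infusion.

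**The relaxation.** In both Flow Charts the row "Safety laboratory parameters incl. urinalysis" carries a version 5.0 footnote at the dosing visits from Cycle 5: footnote 20 in Flow Chart 1 and footnote 12 in Flow Chart 2. Both footnotes describe the procedures as "not mandatory after implementation of CTP version 5.0, but assessments (e.g. hematology & biochemistry laboratory tests, bone marrow aspirates) should be performed" at the investigator's discretion, following standard care. Section 5.2 names 5.2.3 among the procedures reduced from Cycle 5 and adds "Instead, safety assessments should be performed at the investigator's discretion, based on standard medical care". Section 6.2 repeats the reduction and directs sites: "Refer to updated Flow Chart for specific requirements during treatment period".

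**What was left alone.** The row "Eligibility for subsequent cycles of study treatment" has no version 5.0 footnote in either Flow Chart. Vital signs were reduced too, but section 5.2.5.1 and the Flow Chart footnotes expressly keep them mandatory on the day of an infusion.

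**The concern.** A site that opens the Flow Chart, as section 6.2 tells it to, finds that the laboratory before a Cycle 5 or later infusion is optional. A site that opens section 4.1.4 finds that the infusion may not be given unless two results from that laboratory meet stated limits. The first site could omit the count and believe it is compliant.

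The stake is patient safety at the margin. Section 2.3 expects mainly hematologic adverse events, with neutropenia as its example. A low count can be silent, so the adverse-event check that remains at every dosing visit is not a full substitute. There is also a compliance side. The final SAP (07-JAN-2020) postdates the protocol revision (11 SEP 2019). It still lists, as important deviation C2 in Table 6.2:1, continued treatment when the re-treatment criteria are not met, and it cites section 4.1.4 without a cycle limit. A site that skipped the count could not show that it had met that rule.

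**Working it through.** The plan gives no figure to reproduce. The check is a side-by-side reading plus simple counts.

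**1. Dosing-visit columns from Cycle 5.** There are three: Visit 1 and Visit 2 of Cycles 5 and 6 (Flow Chart 1), and Visit 1 of the maintenance cycles (Flow Chart 2).

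| Dosing-visit column | Safety laboratory | Eligibility for next cycles | Vital signs |
|---|---|---|---|
| Cycles 5–6, Visit 1 | footnote 20: optional | footnote 18 only: retained | footnotes 20 and 21: kept on dosing day |
| Cycles 5–6, Visit 2 | footnote 20: optional | footnote 18 only: retained | footnotes 20 and 21: kept on dosing day |
| Maintenance, Visit 1 | footnote 12: optional | footnote 11 only: retained | footnotes 12 and 13: kept on dosing day |

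Safety-laboratory cells made non-mandatory: 3 of 3. Eligibility cells made non-mandatory: 0 of 3. Footnotes 18 and 11 only allow the check to be done up to 2 days early. By contrast, the safety-laboratory cells in Cycles 1–4 and at the End of Cycle 4 (EOC4) visit do not carry footnote 20.

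**2. Is there a reconciling statement?** Section 4.1.4 is not on the list of sections that Amendment 4 says it changed, so its limits stand as written. Sections 6.2.2.4 and 6.2.2.5 still list the laboratory, but both fall under the general reduction announced at the head of section 6.2, so they cannot settle the matter. Amendment 4 also mentions revised Tables 1 and 3, which are not in the available text. I assume that they contain no exception for blood counts.

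**3. Which infusions are exposed?**
- Cycles 5 and 6 are only for patients without progression whose benefit is equivocal: 2 cycles × 2 infusions = 4 at most.
- Section 6.2.2.4 lets tests done at EOC4 serve Cycle 5 Visit 1 when the two visits coincide. That leaves 4 − 1 = 3 infusions without a mandatory count.
- Maintenance brings 1 infusion per 28-day cycle. Section 6.2.2.5 lets EOC4 or end-of-Cycle-6 results serve the first maintenance infusion if it falls within 7 days. EOC4 results always exist under the schedule. End-of-Cycle-6 results exist only if the investigator chose to obtain them.
- The number of patients still on treatment under version 5.0 is not given. The synopsis reports 21 + 6 = 27 entered in Phase I. That is a ceiling, not an estimate.

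**4. Does any analysis depend on these counts?** SAP section 5.1 ends the MTD evaluation period before the third infusion (or 30 days after the last, if there is no third), which is well before Cycle 5. Deviation C2 is found by individual review and excludes nobody. No planned analysis is affected.

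**The case against.** The best counter-argument is that the two rules act at different levels and can both be obeyed. Section 4.1.4 is a condition for dosing; the version 5.0 text relaxes scheduled procedures and data entry. A site can take the count, check it against the limits and leave a passing result out of the eCRF. The unfootnoted eligibility row points the same way, as do section 6.2.2.4's allowance for a Cycle 5 start delayed pending re-treatment eligibility, the retained lists in 6.2.2.4 and 6.2.2.5, and the SAP's later reliance on section 4.1.4. The footnotes are not a bare waiver either: they name hematology among the tests that should still be done under standard care.

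This argument establishes the likely intent. It does not remove the inconsistency. The eligibility row does not cite section 4.1.4. If it means those criteria, it depends on a result that the same chart calls optional. Version 5.0 also wrote an explicit dosing-day exception for vital signs and none for counts, so a site could reasonably infer that counts were meant to go. Standard care does not guarantee a count before each infusion of an investigational antibody.

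A reader might go further and infer that version 5.0 permits dosing below the limits, or that patients were routinely treated without counts. The documents support neither. No text lifts the limits, and nothing shows what sites actually did. A reader might also multiply the maintenance schedule by a number of patients to get a yearly total of exposed infusions. That number is not stated, so any such total would rest on an assumption and would measure no consequence.

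**Conclusion.** The inconsistency is real and minor. Section 4.1.4 requires two counts before every infusion. The Flow Chart footnotes and sections 5.2 and 6.2 make the laboratory that supplies them optional at all three dosing-visit columns from Cycle 5. The exposure is limited to patients still treated under version 5.0 (number not given, at most 27) and to infusions not already covered by the mandatory EOC4 laboratory. Adverse-event assessment remains at every dosing visit, and maintenance is open only to patients who tolerate the infusions. Source laboratory results are open to review under section 8.3.2, so counts that were taken can be checked. The MTD determination and the other planned analyses are untouched.

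The conclusion assumes that Tables 1 and 3, which could not be read, contain no exception for blood counts.

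**What to change.** Add one sentence to Flow Chart 1 footnote 20, Flow Chart 2 footnote 12 and sections 5.2 and 6.2:

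> Neutrophil and platelet counts remain mandatory before each BI 836858 infusion, per section 4.1.4 (up to 2 days before; EOC4 or end-of-Cycle-6 results may be reused as allowed in 6.2.2.4 and 6.2.2.5).

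The 2-day window is the one the Flow Charts already allow for the safety laboratory. The reuse clause is needed because a strict 2-day rule would override the 7-day allowance in section 6.2.2.5. The rest of the panel stays at the investigator's discretion, and passing counts need no eCRF entry.

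The cost is one sentence in four places and no new eCRF field. Section 4.1.4 already requires the counts, so the only downside is that a small part of the intended reduction in patient burden is given back.
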